6.2.2. Adverse Events

AEs will be characterized by type, frequency, severity (as graded by NCI CTCAE version 4.03), timing, seriousness and relationship to study treatment. Adverse events occurring during the 7 day lead in phase for PK will be summarized separately from adverse events reporting after first dose of MK-3475 (C1D1). Baseline signs and symptoms will be recorded at baseline and then reported as adverse events during the trial if they worsen in severity or increase in frequency.

Treatment Emergent Adverse Events

All deaths and serious AEs, regardless of cause, occurring from start of treatment until 28 days after the last dose will be considered treatment-emergent. All other non-serious AEs occurring after treatment start regardless of cause, will be considered treatment-emergent up until 28 days after the last dose or until start of new anti-cancer treatment, whichever occurs first. Disease progression is not considered a treatment emergent AE unless the patient dies of disease prior to 28 days after the last dose. Events that are continuations of baseline abnormalities are considered treatment emergent AEs only if there is an increase in grade over baseline, or if there is an increase following a decrease during the study.

For subjects with a 7 day lead-in phase for PK, adverse events reported during the lead-in phase will only be considered as treatment emergent for the combination if there is an increase in grade after the first dose of MK-3475 (C1D1) or if there is a decrease and then subsequent increase during treatment with the combination.

Treatment Related Adverse Events

Treatment emergent AEs with causality related to treatment, as judged by the investigator, will be considered treatment-related. Events that are continuation of baseline abnormalities are not considered treatment- related unless there is an increase in grade, or if there is an increase following a decrease, and the increase is judged by the investigator to be due to treatment.

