8.3.3.2. Analysis of Secondary Safety Endpoint

Adverse Events

AEs will be graded by the Investigator according to the Common Terminology Criteria for Adverse Events (NCI CTCAE) version 4.03 and coded using the Medical Dictionary for Regulatory Activities (MedDRA). The focus of AE summaries will be on treatment-emergent AEs. The number and percentage of patients who experienced any AE, serious AE (SAE), treatment-related AE, and treatment-related SAE will be summarized according to worst toxicity grades. The summaries will present AEs on the entire study period, separately for the lead-in PK period and by cycle (Cycle 1, Cycle 2 and Cycles beyond 2), as well as for the entire treatment period starting at C1D1 (first dose of MK-3475).

For AE summaries of the treatment period starting at C1D1, treatment-emergent will be defined as an adverse event with an initial onset or increasing severity after the first dose of

MK-3475. For all other AE summaries, treatment-emergent will be defined as an adverse event with an initial onset or increasing severity after the first dose of any study medication (axitinib, in the case of the lead-in PK period).

- An overall summary of AEs will be provided. The number and percentage of patients who experienced any AE, who experienced any SAE, who experienced any treatment-related AE, who experienced any treatment-related SAE, and who discontinued because of an AE will be presented. Treatment-related AEs are those judged by the investigator to be at least possibly related to the study drug (with a cause related to the study drug indicated on the CRF).
- All treatment-emergent AEs will be summarized by MedDRA SOC and preferred term. A summary of AEs by preferred term and maximum CTCAE grade will be presented. A summary of AEs by preferred term and maximum CTCAE grade group (Grade 1-2, Grade 3-4, and Grade 5) will also be presented. Treatment-emergent AEs will also be summarized for each group and pooled across the groups.
- Treatment-related AEs will be summarized by MedDRA SOC and preferred term separately for axitinib, MK-3475 and both. A summary of treatment-related AEs by preferred term and maximum CTCAE grade will be presented. A summary of treatment related AEs by preferred term and maximum CTCAE grade group (Grade 1-2 vs. Grade 3-5) will also be presented. Treatment-related AEs will also be summarized for each group and pooled across the groups.

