- Deaths will be summarized by three time periods (on-treatment vs. within 90 days of end of treatment vs. > 90 days after end of treatment) and cause of death. Deaths that occurred within 28 days after the last dose of study treatment are defined as on-treatment deaths. Death data will also be listed.
- Patients who withdraw from study treatment because of an AE will be listed separately for axitinib and MK-3475. Patient discontinuation will be determined from the end of treatment (EOT) evaluation (where reason for termination is “Adverse Event”) and the specific AE(s) will be determined from the AE CRF page (where action taken is “Withdrawn from Treatment”).
- SAEs and treatment-related SAEs will be summarized by MedDRA SOC and preferred term. Patients who experienced a SAE will be listed.

The following analyses will be performed for AEs of special interest (including, but not limited to, hepatic disorders [ALT, AST and bilirubin], thyroid dysfunction [hypo-/hyperthyroidism], diarrhea, colitis and pneumonitis).

- Hy's Law eDISH scatterplot of Maximum ALT vs. Maximum Total Bilirubin on treatment.

- Hy's Law eDISH scatterplot of Maximum AST vs. Maximum Total Bilirubin on treatment.
- The prevalence of AEs of special interest will be summarized by preferred term and maximum CTC severity grade.
- Descriptive statistics will be presented for time to AE onset (days), time to grade 2 and grade 3/4 AE onset.

For all safety analyses, only descriptive methods will be used without any formal statistical test.

Laboratory Tests

The number and percentage of patients who experienced laboratory test abnormalities will be summarized according to worst toxicity grade observed for each lab assay. The analyses will summarize laboratory tests on the entire treatment period, separately for the lead-in PK period and by cycle (Cycle 1, Cycle 2 and Cycles beyond 2), as well as for the entire treatment period starting at C1D1 (first dose of MK-3475) for patients receiving combination therapy.

For laboratory tests without CTC grade definitions, results will be categorized as normal, abnormal or not done.

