10. APPENDICES

Appendix 1. Programming Specifications for AE Analyses

a. Time to AE onset

1. Definition

Time to AE onset (days) will be calculated as $AE\ start\ date - first\ dose\ date + 1$. The definition and calculations are similar for time to Grade 3/4 AE onset.

AE start date

The Date of Onset for the first occurrence of the AE based on the Log AE CRF page.

First dose date

For AE summaries of the lead-in PK period: The date of the first dose taken from the Axitinib Dosing CRF page.

For AE summaries of the treatment period starting at C1D1: The date of the first dose taken from the MK-3475 Dosing CRF page.

For AE summaries of the entire treatment period (including by cycle): The date of the first dose taken from either the Axitinib or MK-3475 Dosing CRF page, whichever occurs first.

b. Duration of AE

1. Definition

Duration of AE (days) is defined as the cumulative duration across episodes of the specific AE (by preferred terms) where duration for each episode is calculated as $AE\ end\ date - AE\ start\ date + 1$ excluding any overlap. Duration of AE is defined for subjects with the AE.

AE start date

The Date of Onset based on the Log AE CRF page.

AE end date

The Date Resolved based on the Log AE CRF page.

2. Censoring

AE resolution is considered an event (censoring variable=1). If a subject has an AE that was ongoing (does not have to be the last AE) at the time of analysis, the time is censored (censoring variable=0) at the last available on treatment visit date. Subjects who die prior to resolution of the AE will be censored at the *date of death*. If the date of death is the same as the date of the resolution of the AE, the subject will be censored at that date (i.e. resolution will not be considered an event) and only if the AE is the AE that resulted in death will it be counted as an event.

Date of death

[figure not shown]
Death date is based on the Notice of Death CRF page.

3. Clustered Events

[figure not shown]
For clustered events, a patient could have multiple events in the cluster which may overlap. In this case, AE duration will be summed across all events in the cluster accounting for the overlap (i.e. overlapping periods between events in the same cluster are not double-counted). Lags between events in the same cluster are not included in the duration.

The following scenarios provide examples of the calculation for 2 events in the same cluster. The extension to 3 or more events of the same cluster is similar.

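### For the period from C1D1, the SAP measures any-grade time to AE onset from the event's first occurrence, so a lead-in AE that worsens on the combination gets a zero or negative onset time

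*SAP*

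**What the plan says.** SAP Appendix 1a gives the formula: "Time to AE onset (days) will be calculated as" AE start date minus first dose date plus 1. The first dose date changes with the summary period. The lead-in summaries use the first axitinib dose and the entire-period summaries use the earlier of the two drugs. The third case reads: "For AE summaries of the treatment period starting at C1D1: The date of the first dose taken from the MK-3475 Dosing CRF page".

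The AE start date does not change with the period. One definition serves all three: "The Date of Onset for the first occurrence of the AE based on the Log AE CRF page".

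Three places let lead-in events into the C1D1 summaries:

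- SAP 6.2.2 sets out when a lead-in event counts as treatment-emergent for the combination. The condition, applied once MK-3475 has started, is: "if there is an increase in grade after the first dose of MK-3475 (C1D1) or if there is a decrease and then subsequent increase".
- SAP 8.3.3.2 defines treatment-emergent for this period as an event "with an initial onset or increasing severity after the first dose of" MK-3475. The same words recur there for the other summaries, with a different first dose.
- The prevalence rules in SAP Appendix 1c repeat the 6.2.2 conditions for patients with a lead-in.

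The variable is reported for AEs of special interest in SAP 8.3.3.2: "Descriptive statistics will be presented for time to AE onset (days), time to grade 2 and grade 3/4 AE onset".

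**The concern.** An event admitted to the C1D1 summaries because it worsened has, by construction, a first occurrence before C1D1. The formula then subtracts a later date from an earlier one. What qualifies the event for the table is its worsening on the combination, but the time reported is that of its first appearance on axitinib alone. Under the plus-1 convention the smallest meaningful value is 1, so every such value is out of range, and every one errs towards early onset. At stake is the description of how soon AEs of special interest appear once MK-3475 is added.

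**Working it through.** The documents give no figure to reproduce here. The check is date arithmetic on the SAP's own formula.

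**Inputs**

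- Formula and dates: SAP Appendix 1a.
- Lead-in: 7 days of axitinib alone, for all Dose Finding patients and at least 8 Expansion patients (SAP 2.1).
- Planned numbers: about 20 DLT-evaluable Dose Finding patients and about 60 patients in all (SAP 8.1.3).
- Assumption: C1D1 falls on lead-in Day 8. The protocol's Schedule of Activities allows ±3 days at C1D1, so Days 5 and 11 are shown as a range.

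**Step 1: value as written.** Let *d* be the lead-in day of first onset and *c* the lead-in day on which C1D1 falls. Time to onset is *d* - *c* + 1. For any lead-in onset *d* < *c*, so the result is never above 0. With *c* = 8:

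| Lead-in day of onset | 1 | 2 | 3 | 4 | 5 | 6 | 7 |
|---|---|---|---|---|---|---|---|
| Time to onset (days) | -6 | -5 | -4 | -3 | -2 | -1 | 0 |

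With *c* = 5 the values run from -3 to 0 (onset on Days 1 to 4). With *c* = 11 they run from -9 to 0 (onset on Days 1 to 10).

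**Step 2: one patient.** A Grade 1 event starts on lead-in Day 3 and rises to Grade 2 on C1D15, which is lead-in Day 22.

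- C1D1 period as written: 3 - 8 + 1 = -4.
- C1D1 period using the worsening date: 22 - 8 + 1 = 15.
- Entire period as written: 3 - 1 + 1 = 3, a valid value.

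Only the C1D1 summaries are affected. In the lead-in and entire-period summaries the first dose is lead-in Day 1, so a lead-in onset gives at least 1.

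**Step 3: is there a rescue rule?** SAP 7.1 has two negative-duration rules. One concerns dates with a missing day or month. The other resets PFS, TTR, DR and OS to 1 day. Neither reaches a fully recorded AE onset date.

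**Step 4: how many patients could be affected?** 20 + 8 = 28 patients with a lead-in; 28/60 = 47%. This counts patients exposed to a lead-in. To be affected, a patient must also have the event start in the lead-in and then qualify again after C1D1. The documents give no rate for that, so no shift in a median can be calculated.

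**Step 5: which AEs of special interest can start in the lead-in?**

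- Hepatic: the Schedule of Activities places routine chemistry at screening, at lead-in Day 1 (if not done in the prior 7 days) and at C1D1, with none at lead-in Day 7. An abnormality first found and dated at C1D1 gives Day 1.
- Thyroid: tests are at lead-in Day 1. After that, footnote 15 places the next on-treatment TSH at Cycle 2 Day 1.
- Pneumonitis and colitis: Protocol Table 6 handles these as immune-related events of MK-3475, which is not given in the lead-in.
- Diarrhoea: Protocol 1.2.2.2 lists it among the most common axitinib events, so onset in the lead-in with later worsening is plausible.

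**The case against.** The best defence is that the rule can be programmed sensibly. If a programmer first selects the records that are treatment-emergent for the C1D1 period and then takes the earliest, an event that resolved in the lead-in and recurred gets a positive time. Appendix 1b supports this, because it treats one preferred term as several episodes, each with its own onset date. The CRF might also log a worsening as a new row. This stands in part: a reader might infer that all recurrences are mistimed, and the documents do not establish that. It does not dispose of an ongoing event that worsens. Appendix 1a asks for the first occurrence, no worsening date is named anywhere, and the CRF is not among the documents.

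Other stronger readings go further than the text allows:

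- *Grade-specific times are wrong too.* Appendix 1a says only that the grade 3/4 calculation is similar, which most naturally means the first date at that grade. A lower-grade lead-in event that reaches Grade 3 on the combination then gets a correct positive time. Time to grade 2 onset is asked for in 8.3.3.2 but not defined in Appendix 1a. That is a gap, not an error in a stated rule.
- *All the named AEs of special interest are biased.* The laboratory schedule and the attribution to MK-3475 leave mainly diarrhoea.
- *Nearly half the trial is affected.* The 28 of 60 are those with a lead-in; the affected number is unknown and smaller.

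It is also fair to say that the output is descriptive, with no formal test, and that a non-positive value would be easy to see in programming review.

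**Conclusion.** The point holds in limited form. On the literal text, any-grade time to onset in the C1D1 summaries is wrong for a lead-in AE that enters because its grade rises after C1D1, and the SAP has no rule to correct it. The error runs from -6 to 0 days where a positive worsening day belongs, assuming C1D1 on lead-in Day 8, and from -9 to 0 at the widest window considered. The conclusion rests on reading first occurrence as first ever, and on no separate worsening record carrying its own onset date. If the sponsor intends otherwise, the SAP still needs to say so, because two programmers could produce different tables from it.

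The reach is small. It covers descriptive onset statistics in patients who had a lead-in, chiefly for events that can begin on axitinib alone. A reader might infer a threat to the primary endpoint. There is none: DLTs, the MTD and AE incidence do not use this variable.

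**What to change.** In SAP Appendix 1a:

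1. For the C1D1-period summaries, define AE start date as the date of the first new onset, grade increase or recurrence on or after the first MK-3475 dose that makes the event treatment-emergent. Every value is then at least 1.
2. State that time to grade 2 and time to grade 3/4 onset use the date that grade is first reached in the period being summarised.
3. Keep first occurrence for the lead-in and entire-period summaries.

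This brings Appendix 1a into line with SAP 6.2.2, 8.3.3.2 and Appendix 1c. The cost is a sentence or two in the SAP and a programming change, provided the AE page of the CRF records the date of a grade change. That should be confirmed first.

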#### **8.1.4. Time Period for Collecting AE/SAE Information**

The time period for actively eliciting and collecting AEs and SAEs (“active collection period”) for each patient begins from the time the patient provides informed consent, which is obtained before the patient’s participation in the study (ie, before undergoing any study-related procedure and/or receiving investigational product), through and including a minimum of 90 calendar days after the last administration of the investigational product.

For patients who are screen failures, the active collection period ends when screen failure status is determined.

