#### **8.1.4.2. Recording Non-serious AEs and SAEs on the CRF**

During the active collection period, both non serious AEs and SAEs are recorded on the CRF.

Follow up by the investigator may be required until the event or its sequelae resolve or stabilize at a level acceptable to the investigator, and Pfizer concurs with that assessment.

If a patient begins a new anticancer therapy, the recording period for non serious AEs ends at the time the new treatment is started; however, SAEs must continue to be recorded on the CRF during the above indicated active collection period.

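### SAP Appendix 1b censors a living patient's ongoing AE at the last on-treatment visit but counts later resolutions, so a Kaplan-Meier summary of AE duration is biased short

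*SAP*

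**What the plan says.** SAP Appendix 1, part b (Duration of AE) sets three end points for one time variable:

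- **Resolved AE:** resolution is the event. The end date is "The Date Resolved based on the Log AE CRF page", with no limit at treatment stop.
- **Death with the AE unresolved:** "Subjects who die prior to resolution of the AE will be censored at the" date of death, again with no limit at treatment stop.
- **AE ongoing at analysis, patient alive:** "the time is censored (censoring variable=0) at the last available on treatment visit date".

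The SAP does not define an on-treatment visit. Its only day-limited use of the term (section 8.3.3.2) concerns deaths within 28 days of last dose.

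Several passages extend AE observation past treatment:

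- SAP 6.2.2 treats deaths and serious AEs "occurring from start of treatment until 28 days after the last dose will be considered treatment-emergent". Non-serious AEs "will be considered treatment-emergent up until 28 days after the last dose or until start of new anti-cancer treatment, whichever occurs first".
- Protocol 8.1.4 sets active collection "through and including a minimum of 90 calendar days after the last administration of the investigational product", and Protocol 9.6 runs the safety analysis to 90 days after last dose.
- Footnote 19 of the Schedule of Activities and footnote 12 of Appendix 6 record AEs on the CRF only to the Day 28 visit.
- Protocol 8.1.4.2 adds that "Follow up by the investigator may be required until the event or its sequelae resolve or stabilize".

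**The concern.** Whether observed time is kept depends on how the AE turns out. After treatment stops, a resolution on day 40 is counted at day 40 and a death on day 40 is censored at day 40. An AE known to be present on day 40 in a living patient is cut back to a visit that may have been weeks earlier. This is informative censoring created by the derivation. It removes the long, unresolved AEs from the later risk sets, so toxicity looks shorter and more reversible than the data show.

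There is also a boundary problem. An AE can be treatment-emergent with onset after the last on-treatment visit. If it is ongoing, its censoring date can precede its start date.

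**Working it through.** The documents give no figure for AE duration, so there is none to reproduce. The rules come from Appendix 1b. The resolution times, the follow-up actually achieved and the share of AEs that end treatment are my assumptions.

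**1. Direction.** Compare the rule with censoring at the last date the AE was known to be ongoing. The resolution events and their times are the same. Each risk set is the same or smaller, because unresolved AEs leave earlier. Each Kaplan-Meier step d/n is therefore equal or larger, and the curve equal or lower. No distributional assumption is needed.

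**2. Eight AEs.** Four resolve at days 20, 30, 40 and 60. Four are ongoing at day 95, with the last on-treatment visit at day 5.

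- Last-known-status censoring: 7/8, 6/8, 5/8, 4/8. The median is 60 days, with half still unresolved.
- Appendix 1b: the four ongoing AEs leave at day 5, so the curve is 3/4, 2/4, 1/4, 0. The median is 30 days, with all resolved by day 60.

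**3. Worst case: every AE ends all treatment at onset.** Assume exponential resolution with median 60 days, F(t) = 1 − 2^(−t/60), follow-up of c days, and unresolved AEs censored near day 0. The curve then describes resolution time among AEs that resolve within c, and the reported median solves F(t) = F(c)/2.

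- c = 90: F(90) = 0.646, F(t) = 0.323, t = 33.8 days. The correct median is 60.
- c = 28: F(28) = 0.276, F(t) = 0.138, t = 12.9 days. The correct answer is not reached.

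**4. Mixed case.** A share q of AEs ends all treatment at onset. For the rest, remaining treatment time R is exponential with median 180 or 300 days. Follow-up is 90 days past treatment. With λ = ln 2/60, μ = ln 2/(median of R) and S(t) = 2^(−t/60), the fraction at risk under the rule for t ≤ 90 is

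S(t) − q·S(90) − (1−q)·S(90)·[μ/(λ+μ)]·[1 − e^(−(λ+μ)t)].

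All resolutions up to day 90 are seen, so the reported median is where the integral of λS(t)/(at risk) reaches ln 2. For q = 0.20, median R of 180 and t = 52: 0.548 − 0.071 − 0.039 = 0.439 at risk, against 0.548 with correct censoring.

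| Share of AEs ending all treatment | Reported median (true 60) |
|---|---|
| 4.2% | 56.1–57.1 days |
| 10% | 54.6–55.5 days |
| 20% | 52.1–52.8 days |
| 100% | 33.8 days |

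With q between 4.2% and 20%, a true median of 30 days is reported as 29 to 30, and a true 120 as about 90 to 107. The 4.2% is the proportion of patients who stopped single-agent MK-3475 for a related AE (Protocol 1.2.2.4). I use it only as a low value, since the documents give no rate for the combination.

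**5. Which visit counts.** I simulated 6,000 AEs per scenario, all ending treatment within 7 days of onset, with a true median of 60 days. With 90 days of follow-up the reported median is 36 to 37 days if the visit is the last cycle Day 1 or End of Treatment. It is 47 if the Day 28 follow-up visit counts as on treatment. With 28 days of follow-up and that visit counted, the bias disappears.

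**6. Censoring before onset.** The treatment-emergent window runs 28 days past last dose. If End of Treatment (±3 days) is the last qualifying visit, onset can follow it by up to about 28 + 3 = 31 days. If only 21-day cycle visits qualify, the gap can be about 21 + 28 = 49 days. An AE in that gap that is still ongoing gets a zero or negative time. SAP 7.1 does not repair this: it deals with missing dates, and its 1-day reset names only PFS, TTR, DR and OS.

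**The case against.** The SAP body lists no AE-duration result. Section 8.3.3.2 asks for time to onset and prevalence for AEs of special interest, so a Kaplan-Meier median of duration is an inference. That is fair. But Appendix 1b defines a censoring variable for duration, and SAP 8.2 assigns Kaplan-Meier to time-to-event endpoints. Anyone programming from the appendix would produce the biased quantity.

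The discarded follow-up may also be short. For non-serious AEs, follow-up past the collection period is only something that may be required, recording stops at new anticancer therapy, and two schedule footnotes end CRF recording at Day 28. If that is the practice, and the Day 28 visit counts as on treatment, little is lost. This stands as a limit on size. It rests on a visit definition the SAP does not give and on the shorter of two conflicting collection periods.

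For patients still on treatment the rule is reasonable, and cut-back times are flagged as censored. Both are true. The flag does not help, because Kaplan-Meier assumes that censoring is unrelated to outcome.

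A reader might infer that immune-related AEs are the worst affected and that RP2D selection is distorted. The documents do not support this. A patient who stops one drug for toxicity may continue the other (Protocol 3.1 and 6.4), so on-treatment visits can go on. The MTD rests on DLT counts, no stated rule feeds AE duration into the RP2D, and SAP 8.3.3.1 lists each DLT's time to resolution by patient.

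**Conclusion.** The rule is wrong as written and should be corrected, at modest priority. The direction is certain for any Kaplan-Meier summary of AE duration: equal or shorter, never longer, than with last-known-status censoring.

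The size depends on how many AEs end all study treatment, which the documents do not give. With exponential resolution, a true median of 60 days and 90 days of off-treatment follow-up, the reported median is about 52 to 57 days for shares of 4% to 20%. It would be tempting to say that reported durations are roughly halved, but the 34-day figure needs every AE in the summary to end all treatment at onset. It is a worst case.

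Censoring before onset is conditional. It arises if the on-treatment visit excludes the Day 28 follow-up visit, and only for ongoing treatment-emergent AEs that start after the last qualifying visit.

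**What to change.** Replace the censoring date in SAP Appendix 1b. An AE ongoing at analysis in a living patient should be censored at the last date its status was recorded: the last AE assessment or visit, including post-treatment follow-up. That date should be no earlier than AE onset, and no later than the data cut-off or the end of the AE recording period. Apply the same cut-off to resolutions, so that one falling after it is treated as ongoing at the cut-off. Keep the death rule. State which recording period applies, since the protocol gives both Day 28 and 90 days.

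The cost is one changed date derivation. The appendix names only onset and resolution dates from the AE log, so a status date may not be held there. In that case the last visit or contact date can stand in for it.

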[figure not shown]
- **TWO EVENTS OF THE SAME CLUSTER WHERE ONE EVENT COMPLETELY CONTAINS THE OTHER EVENT**

- **CERTAIN PORTIONS OF TWO EVENTS IN THE SAME CLUSTER OVERLAP**

[figure not shown]

- **TWO EVENTS OF THE SAME CLUSTER ARE CONTIGUOUS TO EACH OTHER**

$$duration = enddate2 - startdate1 + 1$$

- **TWO EVENTS OF THE SAME CLUSTER ARE NON-OVERLAPPING**

$$duration = (enddate1 - startdate1 + 1) + (enddate2 - startdate2 + 1)$$

c. AE Prevalence

1. Definition

AE prevalence is defined as the number of patients with an AE in a particular time period (including both new cases with an onset date during the specified time period AND cases with an AE continued from a previous time period) divided by the number of patients at risk during the specified time period. The number of patients at risk includes all subjects except those who either have discontinued or died prior to the specified time period.

AE prevalence will be presented for the entire study period, separately for the lead-in PK period and by cycle (Cycle 1, Cycle 2 and Cycles beyond 2), as well as for the entire treatment period starting at C1D1.

2. Assumptions

For AE summaries of the study period starting at C1D1 the following apply:

- A patient is counted in the numerator if the patient has an onset date of the AE during Cycle 1 OR for patients with a 7 day lead-in PK period there is an increase in grade of the AE after the first dose of MK-3475 (C1D1) or if there is a decrease and then subsequent increase during treatment with the combination.
- The denominator will include subjects who have received at least one dose of MK-3475.

For AE summaries of the entire study period including by cycle (Lead-in PK period, Cycle 1, Cycle 2 and Cycles beyond 2) the following apply:

- Patients are counted for an AE in each cycle up until the cycle where the AE resolved. Thus, the calculation conservatively assumes that if the AE resolved in a cycle, it resolved at the end of the cycle.
- For Lead-in PK period, a patient is counted in the numerator if the patient has an onset date of the AE during the Lead-in period.
- For Cycle 1, a patient is counted in the numerator if the patient has an onset date of the AE during Cycle 1 OR an onset date during the Lead-in PK phase that is still ongoing in Cycle 1 (did not have a resolution date in the Lead-in phase).

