- For Cycle 2, a patient is counted in the numerator if the patient has an onset date of the AE during Cycle 2 OR an onset date during the Lead-in PK phase or Cycle 1 that is still ongoing in Cycle 2 (did not have a resolution date in the Lead-in phase or Cycle 1).

- For Cycles ≥ 2 , a patient is counted in the numerator if the patient has an onset date in Cycles ≥ 2 OR an onset date in a previous cycle that is still ongoing (did not have a resolution date in Cycle 1 or earlier).
- The denominator for a particular time period will include subjects who are at risk prior to the time period. The number at risk includes all subjects except those who either have discontinued (based on the 'Subject Summary' CRF) or died prior to the specified time period (i.e. Death Date based on 'Notice of Death' CRF is prior to start of time period).

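### The SAP's AE prevalence rule for the period from C1D1 counts new onsets only in Cycle 1, against its own definition, and so undercounts later AEs in that summary

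*SAP*

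**What the plan says.** SAP Appendix 1, part c, defines AE prevalence for a period as a proportion. The denominator is patients at risk and the numerator is patients with the AE, "including both new cases with an onset date during the specified time period AND cases with an AE continued from a previous time period". The periods to be reported are the entire study, the lead-in, Cycle 1, Cycle 2 and Cycles beyond 2, "as well as for the entire treatment period starting at C1D1".

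For that last period the assumptions give this numerator: "A patient is counted in the numerator if the patient has an onset date of the AE during Cycle 1 OR for patients" who had a lead-in, the AE rises in grade after the first MK-3475 dose, or falls and then rises on the combination. The denominator is stated separately: "The denominator will include subjects who have received at least one dose of MK-3475".

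Two places in the body of the SAP bear on this:

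- Section 8.3.3.2: "For AE summaries of the treatment period starting at C1D1, treatment-emergent will be defined as an adverse event with an initial onset" or worsening after the first MK-3475 dose. It sets no cycle limit.
- Section 6.2.2, on patients with a lead-in: "adverse events reported during the lead-in phase will only be considered as treatment emergent for the combination if there is an increase in grade". The rise must come once MK-3475 has started; a fall and later rise on the combination also qualifies.

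Prevalence by maximum grade is a planned summary for AEs of special interest (SAP 8.3.3.2): hepatic disorders, thyroid dysfunction, diarrhea, colitis and pneumonitis among them.

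**The concern.** The period runs from C1D1 to the end of treatment and the denominator matches that, but the numerator admits new onsets from the first three weeks only. Appendix 1 is a programming specification, so it may well be coded literally.

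The affected events are ones for which late onset is expected. Protocol 5.2.7.4 says immune-related AEs may appear soon after the first dose or months after the last, and protocol 5.2.4.2 sets MK-3475 treatment at 24 months. A whole-period prevalence of, say, colitis or pneumonitis that leaves out onsets after Cycle 1 would look more favourable than the data.

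**Working it through.** The documents give no prevalence figure to reproduce. The check compares the texts and then illustrates the size under stated assumptions.

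**Which patients the rule misses**

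| First onset of the AE | Definition, whole period from C1D1 | Rule as written |
|---|---|---|
| Cycle 1 | counted | counted |
| Cycle 2 or later, no lead-in | counted | not counted |
| Cycle 2 or later, had a lead-in | counted | not counted if the grade-change condition covers only AEs that began in the lead-in (as in SAP 6.2.2); counted if a new AE is read as a rise from grade 0 |

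The rule is not a Cycle 1 rule misplaced under another label. Cycle 1 has its own rule further down, which opens with almost the same words, so a copying slip is likely.

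**How many patients have no lead-in**

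Inputs: 20 dose-finding and 40 expansion patients (SAP 8.1.3); lead-in for all dose-finding patients and at least 8 expansion patients (protocol 3.1); 10 evaluable patients at the MTD (SAP 8.1.1).

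- Expansion patients without a lead-in: at most 40 − 8 = 32, and 32/40 = 80%.
- With 10 dose-finding patients pooled at the MTD: 32/50 = 64%.
- Whole study: 32/60 = 53%.

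**Share of first onsets that fall in Cycle 1**

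Assume exponential time to onset with median m weeks. Cycle 1 lasts 3 weeks, so the share is f = 1 − 2^(−3/m).

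| m (weeks) | 2 | 6 | 12 | 24 | 68 |
|---|---|---|---|---|---|
| f | 0.646 | 0.293 | 0.159 | 0.083 | 0.030 |

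This counts onsets over unlimited time. Restricting to onsets within an assumed 52 weeks divides f by 1 − 2^(−52/m). The share becomes 0.159/0.950 = 17% for m = 12, 0.083/0.777 = 11% for m = 24 and 0.030/0.411 = 7% for m = 68.

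On the generous reading, where every later onset in the 20 + 8 = 28 lead-in patients is counted, the share captured is (28 + 32f)/60: 0.811 for m = 2 and 0.483 for m = 68.

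A second model has limited follow-up built in. Assume a constant onset probability h per cycle over K cycles, no dropout and no lead-in AEs. The rule counts h and the definition counts 1 − (1 − h)^K.

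- K = 4, h = 5%: 0.05/0.1855 = 27% of affected patients counted.
- K = 17, h = 1%: 0.01/0.1571 = 6%.
- K = 8, h = 2%, 60 patients: 60 × 0.02 = 1.2 counted, against 60 × 0.1492 = 9.0.

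**Worked example (assumed counts)**

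Take 40 patients who all stay at risk, with no lead-in AEs, and the narrower reading of the grade-change condition. Two have an AE that starts and resolves in Cycle 1, two have one that starts and resolves in Cycle 2, and four have a first onset in Cycle 3 or later.

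- Definition, period from C1D1: 8/40 = 20%.
- Rule as written: 2/40 = 5%.

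**Related slip in the same appendix**

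The reported column is Cycles beyond 2, but the rule is written for Cycles ≥2: onset in those cycles, or an earlier AE that "did not have a resolution date in Cycle 1 or earlier". An AE confined to Cycle 2 is thus counted under Cycle 2 and again in the later column. In the example that column shows (2 + 4)/40 = 15% where it should show 4/40 = 10%.

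**Separate slip in SAP 8.3.3.2, concomitant medications**

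For patients without a lead-in, a drug is concomitant if it is ongoing at the end of study or has a stop date before C1D1. A drug both started and stopped during treatment is then neither previous (it started too late) nor concomitant. Protocol 9.6.3 treats every drug received during treatment as concomitant.

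**The case against.** The best defence is that this is a drafting slip with the intent visible nearby, in one descriptive table on which no decision rests. Later AEs also appear in the treatment-emergent tables for the period from C1D1, in by-cycle prevalence and in time to onset. Prevalence for the entire study period adds a further safeguard: for patients without a lead-in that period is the same window, and the Cycle 1 limit is not among its rules. All of this stands. It bounds the harm but does not make the rule right: a programmer who follows it gets a wrong number, and one who quietly corrects it departs from the SAP.

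The sizes can also be challenged. The onset medians are assumed, the unlimited-time formula understates capture at long medians (7% rather than 3% at 68 weeks with 52 weeks of follow-up), and 32 is a maximum because the protocol sets only a minimum of 8 expansion lead-ins. That is fair. Only the direction of the error is established.

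A whole-period percentage below that of a single cycle would not by itself reveal this error. By-cycle denominators drop patients who have discontinued or died, and by-cycle Cycle 1 includes lead-in AEs that continue unchanged, so the same pattern can arise under correct rules.

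Leaving unchanged lead-in AEs out of the C1D1 summary also departs from the general definition, but it agrees with SAP 6.2.2 and looks deliberate. The Cycle 1 limit has no such support.

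**Conclusion.** The concern holds. As written, the numerator for the period from C1D1 contradicts the SAP's own prevalence definition and does not match its denominator. The error can only lower the reported prevalence. It affects up to 32 of 40 expansion patients on any reading, and lead-in patients too if the grade-change condition is read as SAP 6.2.2 suggests.

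How far the figure falls depends on onset timing, which the documents do not give. Under the assumptions above, Cycle 1 captures from about two thirds of first onsets down to a few per cent; the generous reading raises this to between 81% and 48% across all 60 patients.

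The damage is confined to one secondary safety summary. It should be corrected because that summary covers the immune-related events for which late onset is expected. The Cycles ≥2 rule and the concomitant-medication rule are also wrong as written, but are separate from the main point.

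**What to change.** Three wording corrections in the SAP:

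1. Appendix 1, part c, period from C1D1: count an AE with onset on or after the first MK-3475 dose and within the treatment-emergent window. Apply the grade-change condition only to AEs that began in the lead-in.
2. Appendix 1, part c, later cycles: replace the Cycles ≥2 rule with one for Cycles >2, counting onset in Cycle 3 or later, or earlier onset not resolved by the end of Cycle 2.
3. Section 8.3.3.2, concomitant medications: for patients without a lead-in, make the stop-date condition on or after C1D1.

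When making the first change, name the window. SAP 6.2.2 ends it 28 days after the last dose, while protocol 9.6 extends the safety analysis to 90 days; AEs arising later than the chosen window would still be left out of this summary.

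The cost is a short SAP revision. No new data are needed, and patient management and the primary analysis do not change.
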